## List of Abbreviations

AuToDeCRA-2	Autologous Tolerogenic Dendritic Cells for Rheumatoid Arthritis (2 nd phase trial)
AE	Adverse Event
ANOVA	Analysis of Variance
AR	Adverse Reaction
bDMARD	Biological Disease-modifying antirheumatic drug
CI	Chief Investigator
CRP	C-reactive protein
csDMARDs	Conventional synthetic disease modifying anti-rheumatic drugs
CTIMP	Clinical Trial of an Investigational Medicinal Product
DHRs	Drug Hypersensitivity Reactions
DMARD	Disease-modifying antirheumatic drug
ESR	Erythrocyte Sedimentation Rate
GCP	Good Clinical Practice
GVHD	Graft Versus Host Disease
HLA	Human Leukocyte Antigen
LMW	Low Molecular Weight
MHRA	Medicines and Healthcare products Regulatory Agency
NuTH	The Newcastle upon Tyne Hospitals NHS Foundation Trust
PICS	Patient Identification Centres
PI	Principal Investigator
PLNA	Popliteal Lymph Node Assay
RA	Rheumatoid Arthritis
REC	Research Ethics Committee
RGF	Research Governance Framework for Health and Social Care: Second Edition
SAE	Serious Adverse Event
SOP	Standard Operating Procedure
Swollen Joint Count	SJC
Tender Joint Count	TJC
TGN 1412	Trial name for a type of monoclonal antibody therapy manufactured by German firm TeGenero
UAR	Unexpected Adverse Reaction

## STUDY SUMMARY

Study Title	Development of an in vitro assay for drug safety and efficacy and skin sensitivity
Internal ref. no. (or short title)	Safety testing of novel compounds and drugs
Study Design	Laboratory
Study Participants	Healthy Volunteers / Rheumatoid Arthritis (RA) Patients /Surgical Patients ( Sub-Studies )
Planned Size of Sample (if applicable)	
Healthy Volunteer          Recruit 4-6 participants per week          1 set of skin punch biopsy (2 biopsies per set) per healthy volunteer          60-70ml blood per healthy volunteer          For patients who have opted in to consent to provide further samples a maximum of 3 sets of skin punch biopsies (2 biopsies per set) and 3 sets of 70 ml of blood.
 
Sub-Study : Rheumatoid Arthritis Patients          Recruit 40-50 per 12 months, 80-100 over 24 months          1 x 60-70ml blood and further maximum 120ml in serial (20ml x 6 blood samples)
 
Sub-study :Surgical Patients          1x 70ml blood at pre-surgical clinic visit          Excess skin sample taken at time of surgery ( minimum 2x 4mm)

Follow up duration (if applicable)	NA
Planned Study Period	5 years
Research Question/Aim(s)	The development and use of in vitro skin assays to predict adverse responses to compounds including drugs and cellular therapies
Funder and financial and non-financial support given	
Alcyomics Ltd - Payment of research staff, research nurses, funding study consumables, vouchers for participants.
 
Vouchers  Healthy Volunteer:
 
 
£50.00 voucher for 1 set of skin biopsies (2 biopsies per set) and 1 set of 70ml blood sample
 
 
For patients who have opted in to consent to provide further samples:
 
 
£25.00 voucher per 70 ml blood sample and £25.00 voucher per 1 set of skin punch biopsy (2 biopsies per set)
 

	
 
• A maximum of £150.00 for blood and skin punch biopsies samples
 
 
Rheumatoid Arthritis Patients Sub Study 1
 
 
• £50.00 voucher for skin biopsies (x2) and 1x blood sample
 
• £25.00 voucher per blood sample ( )
 
• A maximum of £150.00 for a series of blood samples
 
 
Rheumatoid Arthritis Patients Sub Study 2
 
 
• £25.00 voucher per blood sample
 
• A maximum of £150.00 for a series of blood samples
 
 
Surgery Patients Sub Study 3
 
 
• £25.00 voucher per blood sample
 

Role of study sponsor and funder	Alcyomics Ltd is responsible for the study design, conduct, data analysis and interpretation, manuscript writing, and dissemination of results and controls the final decision regarding any of these aspects of the study.
Key Words:	Safety and efficacy drug testing ; immunotoxicology; adverse immune reactions ; in vitro pre-clinical testing, novel diagnostics

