### **3.2 Sub-Study – Rheumatoid Arthritis (RA) Patients**

[figure not shown]
**Sub-study Group (1).** PBMC and skin biopsies obtained at a single time-point from 6-10 RA patients will be used to assess the safety of peptides as described for healthy volunteers (above in 3.1).

**Sub-study Group (2).** A cohort of 40-50 RA patients will be assessed for anti-drug antibody responses before and after antibody therapy over two years. This will involve a 70ml peripheral blood sample being taken pre-treatment (baseline) and 20ml blood sample being obtained post-treatment (12, 24, 36, 48, 60, 72, weeks). Skin biopsies will not be required from volunteers in this group.

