#### **Rheumatoid Arthritis (RA) Patients**

Our target populations of RA patients will be enrolled according to distinct but overlapping criteria to account for two pre-defined sub-study groups as follows:

Sub-study Group (1). RA patients known to have one of the following tissue types: HLADRB0401 or 0404 positive, irrespective of their background DMARD therapy.

Sub-study Group (2). RA patients being started on one of four classes of biologic DMARD (bDMARD; namely anti-TNF, anti-IL-6R or anti-CTLA4 or anti-CD20) that they have not previously received. Such patients will have experienced an inadequate response to conventional synthetic disease modifying anti-rheumatic drugs (csDMARDs), and may also have experienced an inadequate response to one or more treatment with a bDMARD (in one of the aforementioned classes) and/or targeted janus kinase inhibitor DMARD (tDMARD).

The number of RA subjects will be maximum of 40-50 per annum.

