#### RA Patients

Months 1-18:

- Recruitment of patients
- Data Collection
- Disease activity calculations

Months 18-24:

- Data Analysis Correlation with clinical outcomes

Month 24: Completion of study

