## 8.3 End of Study

The study will terminate when the required number of patients have been enrolled and have completed follow-up.

However, the study will end prematurely if

- The Ethics Committee mandate so
- The sponsor mandates so

The approving REC will be notified in writing if the study has been concluded or terminated early.

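### The planned number of RA patients is 80-100 in the Study Summary but 46-60 in section 3.2, and no section reconciles the two

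*Protocol*

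**What the plan says.** The Protocol gives figures that bear on the number of RA patients in four places, and makes the end of the study depend on a number in a fifth.

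- **Study Summary, planned sample size:** "Recruit 40-50 per 12 months, 80-100 over 24 months". The line covers RA patients as a whole and is not split by group.
- **Section 3.2, Group 1:** "PBMC and skin biopsies obtained at a single time-point from 6-10 RA patients".
- **Section 3.2, Group 2:** "A cohort of 40-50 RA patients will be assessed for anti-drug antibody responses before and after antibody therapy over two years".
- **Section 5.1:** "The number of RA subjects will be maximum of 40-50 per annum". This too is not split by group.
- **Section 5.3, RA patients:** recruitment is listed only under months 1-18. Months 18-24 are for analysis, and the entry for the end is "Month 24: Completion of study".
- **Section 8.3:** "The study will terminate when the required number of patients have been enrolled and have completed follow-up". No number is given there.

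**The concern.** The Summary and section 3.2 each read as the plan for the same patients, yet they give totals that cannot both be right. The annual figure in 5.1 matches the Summary's yearly rate, but 5.3 allows 18 months of recruitment where the Summary counts 24.

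Three things depend on the answer. The end rule in 8.3 needs a number, and for RA a reader has to choose between incompatible ones. Patient burden scales with it: each Group 2 patient gives up to 70 + 6 x 20 = 190 ml of blood over 72 weeks, and an ethics committee cannot tell from the text how many patients it has approved. Any later statement that the RA part recruited to plan would also depend on which section is read.

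**Working it through.** **Inputs.** Summary: 40-50 per 12 months and 80-100 over 24 months. Section 3.2: Group 1 6-10, Group 2 40-50. Section 5.1: at most 40-50 RA patients a year. Section 5.3: 18 months of RA recruitment, completion at month 24. No power or precision calculation is given for the RA sub-studies, and none is needed to compare stated counts.

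**1. The Summary's own figure.** Rate x duration: 40 x 2 = 80 and 50 x 2 = 100. The Summary agrees with itself.

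**2. Total from section 3.2.** Group 1 + Group 2: 6 + 40 = 46 and 10 + 50 = 60.

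**3. Summary against 3.2, both groups in each.** 80/46 = 1.74 and 100/60 = 1.67. The lowest Summary figure (80) exceeds the highest 3.2 figure (60) by 20 patients, so rounding does not explain the gap.

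**4. Ceiling from 5.1 with 5.3.** Annual maximum x window, pro rata: 40 x 18/12 = 60 and 50 x 18/12 = 75. The Summary exceeds this by 80/60 = 100/75 = 1.33. Put the other way, 80-100 needs two full years at the maximum rate, and 5.3 lists one and a half.

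| Source | RA total |
|---|---|
| Summary | 80-100 |
| 3.2, Groups 1 + 2 | 46-60 |
| 5.1 with 5.3, derived ceiling | at most 60-75 |

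**5. Does the calendar settle the number?** Group 2 has a "20ml blood sample being obtained post-treatment (12, 24, 36, 48, 60, 72, weeks"). With 365.25/12 = 30.44 days to a month, 72 weeks is 72 x 7/30.44 = 16.6 months. To finish by month 24, a patient must enter by month 24 - 16.6 = 7.4. With uniform accrual from month 0, the RA intake by then is 40/12 x 7.4 to 50/12 x 7.4, about 25-31 patients. That is below every stated total. If intake were front-loaded, the whole first-year maximum of 40-50 could enter by month 7.4. That would still fall short of the Summary, which leaves 80 - 10 = 70 to 100 - 6 = 94 patients for Group 2. So the month-24 date does not supply the missing number.

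**The case against.** Several points on the other side are fair.

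- **The figure in 5.1 is a ceiling, not a target.** This stands. The 60-75 is derived here and stated nowhere in the Protocol, and it is compatible with 46-60. A reader might infer three rival totals, but there are two stated totals and a ceiling that the Summary does not fit.
- **The annual maximum need not be applied pro rata.** If a full second-year allowance could be used in months 13-18, then 80-100 could be enrolled in 18 months. That is arithmetically possible, but the Summary itself spreads the number over 24 months. The conflict with 3.2 is untouched.
- **The two years in 3.2 may be the assessment period.** This is the more natural reading, given visits to week 72. It does not help: 3.2 still describes one cohort of 40-50, with no second intake.
- **The RA work is a secondary objective of a laboratory study, with no stated hypothesis.** This stands and lowers the weight of the point.

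Some stronger readings are tempting, but the documents do not support them. One might call the discrepancy a factor of two, from 80/40 and 100/50. That sets all RA patients against Group 2 alone. One might infer that the gap lets the sponsor stop after seeing results. Section 5.3 places analysis after recruitment, and 8.3 separately lets the sponsor end the study early, so fixing the number would not change that. One might also attach a loss of precision for anti-drug antibody rates, overall or by drug class. Those antibodies are followed only in Group 2, the all-RA totals are the wrong denominator, and the Protocol gives no expected rate, no split by class and no class-level estimate.

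**Conclusion.** The planned RA sample size contradicts itself. The Summary's 80-100 is about 1.7 times the 46-60 in section 3.2, and this rests on stated counts alone. It also exceeds the 60-75 ceiling from 5.1 and 5.3 by a third, assuming that the annual maximum applies pro rata over 18 months. Nothing in the Protocol reconciles the figures, so the required number in 8.3 has no single value for RA.

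This is a wrong figure as written that should be corrected. It is of moderate weight, because it concerns a secondary sub-study with no stated power. Section 8.3 covers the whole study, so the RA figures are only part of what it leaves open: healthy volunteers have only an annual maximum of 300, and surgical patients have no number.

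**What to change.** The sponsor should confirm one number for each RA sub-study and use it consistently in the Summary, 3.2, 5.1 and 5.3.

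- If the 3.2 figures are the real target, correct or delete the 80-100 over 24 months in the Summary and show Groups 1 and 2 separately there.
- If 80-100 is the real target, correct 3.2 and the recruitment window in 5.3. The 72-week follow-up and the month-24 completion should then be checked against it.

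In either case, 8.3 should refer to the confirmed numbers for the RA part of the study. The RA figure should not be made the required number for the whole study, since that would leave the other populations undefined.

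The cost is Protocol wording. If 46-60 is confirmed, no patients are added, but the stated size becomes less favourable than the Summary now suggests.

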## **1. BACKGROUND**

The main aim of the study is to use an *in vitro* human skin based assay that will enable drug sensitivities and allergies to be detected at the early stage of drug development i.e. before animal or human trials.

Animal models provide only a partial guide to drug responses in man and drug companies are becoming increasingly reliant upon human tissue-based assays to improve drug development and bring drugs closer to market in a shorter period of time, thus ultimately reducing drug costs.

The drug trial conducted at the Northwick Park Hospital in 2006 made shocking headlines when a serious incident occurred in human volunteers. It was reported that TGN 1412 was tested on monkeys at doses 500 times greater than that given to the volunteers, but the human test subjects became critically ill within minutes of being given the drug.

An interim report issued by the Medicines and Healthcare products Regulatory Agency (MHRA) notes that the volunteers had a life-threatening incident of cytokine-release syndrome, which occurs when the substances released by the immune cells produce a type of systemic inflammatory response. This was an extreme example of what can go wrong when new drugs are introduced to man for the first time. This exemplifies the need for more effective human drug safety testing.

This is especially true when one considers the increasing number of biological drugs (e.g. monoclonal antibodies and cellular therapies) planned or in development. The problem is compounded by the lack

of effective *in vitro* models and the continued reliance on animal testing. This is one of the reasons that 90% of compounds that drug-makers take into human clinical trials ultimately fail to become viable medicines, and occurrences like the one described above are a very real threat.

Alcyomics Ltd is looking to offer solutions to these problems, which will help pharma and biotech companies to be more innovative while at the same time decreasing their risk of failure. Current expertise will enable us to test drugs for potential allergic or hypersensitivity reactions, including individual responses to stem cells and cellular therapies.

In addition, a large number of low molecular weight (LMW) drugs fail in clinical development. Lack of efficacy along with drug hypersensitivity reactions (DHRs) are a major cause of failure or withdrawal of new LMW drugs (Hay et al., 2014). Despite a battery of clinical and pre-clinical tests used for evaluating the safety of drugs, DHRs are often undetected until drugs are tested in large clinical trials or marketed (Pourpak et al., 2008). This late failure of drugs due to DHRs clearly indicates the need for predictive tools during the early stages of pre-clinical drug development. DHRs can be divided into 2 main groups, allergic reactions caused by adaptive immune mechanisms and non-allergic reactions not involving adaptive immune responses. The latter is the more common type of a DHR response and is often predictable, dose-responsive, and can be observed pre-clinically. In contrast, allergic drug reactions are rarely observed during pre-clinical drug development. There are currently no *in vitro* pre-clinical tools available which have been validated to screen for potential allergic DHRs. However, there are some *in vivo* models such as the modified popliteal lymph node assay (PLNA) (Warbrick et al., 2001, Pieters, 2001), the lymph node proliferation assay (LNPA) (Weaver et al., 2005) and the mouse allergy model (Whritenour et al., 2014, Zhu et al., 2015), which show some potential for predicting DHRs. Drug hypersensitivity can be related to genetic predisposition (Pirmohamed, 2006) occurring in only a minority of the population and therefore can be difficult to predict, especially using animal models (Bala et al., 2005). Consequently, *in vitro* testing using human material may be an attractive alternative. Tests developed more specifically for determining sensitisation potential of topically administered chemicals/compounds such as the human cell line activation test (h-CLAT), direct peptide reactivity assay (DPRA) or KeratinoSens™, (Nukada et al., 2012, Gerberick et al., 2004, Emter et al., 2010) could be potentially further investigated as suitable tools for predicting DHRs for systemically administered compounds.

In order to further develop the skin assay Alcyomics is developing a human *in-vitro* 3D skin model using healthy volunteer skin cells (keratinocytes and fibroblasts) to form 3D skin model for testing in a 96 well format. The objective of our study is to use and evaluate a human *in vitro* skin explant assay for predicting DHRs to drugs, chemicals, cosmetics, biologics and peptides. The skin explant assay used in these studies was modified from the original predictive test, which has been extensively used to understand the underlying mechanism and immunobiology of graft versus host disease (GvHD) ([name] et al., 1999, [name] et al., 1988, Vogelsang et al., 1985), ([name] et al., 2002, Jarvis et al., 2002, Ruffin et al., 2011, Mavin et al., 2012, [name] et al., 2015). The modified assay (commercially known as Skimune®) has been used as a method for predicting skin sensitisation potential of chemical compounds ([name] et al., 2016). It has also recently been extended to test systemically administered LMW drugs that are associated (or not) with hypersensitivity reactions in the clinic. As previously described by [name] and colleagues, the assay is used in an autologous setting, when the different cell types and skin used in the assay are derived from the same donor. The assay involves isolation of peripheral blood mononuclear cells and separation of monocytes to derive dendritic cells which are activated with the compound (or peptide) of interest. The assay can then assess T cell proliferation, cytokine release, and histopathological damage to skin tissue due to any adverse immune reaction. The severity of the skin reaction is scored in severity from grade I-IV (Lerner et al., 1974) and a score of a grade II or above is used to predict a positive DHR.

In addition the assay can be used to predict any adverse immune reactions due to monoclonal antibody therapy – in this regard peripheral blood mononuclear cells are added directly onto autologous skin in the presence or absence of the test monoclonal.

We also aim to use the assay including the 3D skin assay for sensitivity testing other types of compounds e.g. cosmeceuticals which if the results is successful may reduce animal resting in the future and enable the design of safer drugs and compounds.

### **Sub Study- Rheumatoid Arthritis (RA) Patients**

We also aim to extend the study to a small group of RA patients in order to:

1) Test peptides in the skin assay by activating autologous dendritic cells with the peptide of interest and testing on autologous skin samples. These peptides are of potential value in novel RA clinical trials and the assays will allow assessment of dose response as well as safety.

2) Develop assays to assess which biologic will work most efficiently for an individual patient and assess the effect post-therapy.

The background and rationale for this study is as follows:

1) The use of peptides in a local phase II clinical trial AuToDeCRA-2 (Principle Investigator [name]) will commence late 2019/early 2020. The peptides and dose response for instigation in the clinical trial will be tested in healthy volunteers and RA patients who have a particular HLA genotype for peptide recognition.

2) Due to the number of biologic therapies available to rheumatologists for the treatment of RA Patients, there is a critical need for better tools to inform RA disease management. The ability to identify patients, including to respond to first time biologics prior to their treatment would allow tailored therapies for an individual patients (Thomson, Lescarbeau et al. 2015, Smolen, Aletaha et al. 2016).

Alcyomics aims to develop *in-vitro* assays using only blood samples from RA Patients to assess their response to a number of biologics prior to therapy ultimately enabling therapy to be chosen by the clinician on an individual patient basis. This is especially due to some patients developing anti-drug antibodies which neutralise the therapy and therefore negate the treatment. We will therefore aim to develop an *in vitro* test for predicting the potential to develop anti-drug antibodies in individual RA patients (Moots , Xavier et al 2017) .

## **2. STUDY OBJECTIVES**

### **2.1 Primary Objectives**

- Use an *in vitro* human skin based assay that will enable drug sensitivities to be detected at the early stage of drug development i.e. before animal or human trials. To extend and improve our current skin explant assay technology by researching a new assay using 3D skin modelling and bio printing which will enable capacity building and standardisation for use to the pharmaceutical industry for drug safety testing
- Results enable assessment of target genes. This may lead to the identification of novel protein targets for therapeutic purposes.
- Further develop the assays to enable a reduction in animal testing as required by EU legislation (European Directive 86/609/EEC and the 7th Amendment to the Cosmetics Directive (Directive 76/768/EEC2).
- Enable the development of a novel assay for atopic dermatitis drug testing
- 

### **2.2 Secondary Objectives– Rheumatoid Arthritis (RA) Patients**

- Sub-study 1: To assess the safety of peptides for potential use in clinical trial.
- Sub-study 2: To assess the responses of RA patients to biologics and monitor the response post therapy.

## **3. STUDY DESIGN**

### **3.1 Healthy Volunteers**

- Assays will be conducted in the laboratory to assess the effect of the novel drugs or compounds on healthy volunteer blood or tissue.
- A minimal of 6 volunteers will be tested per compound at various dilutions in order to assess potency and effect of the compound on the blood or tissue.
- Lymphocyte proliferation ( known as T cell responses) will be measured as a surrogate to the potential proliferation of T cells and thus adverse effect of the drug on the healthy volunteer.
- The skin biopsy will be assessed for histopathological damage due to the effect of the T cells on the skin.
- Results from the assays (n=6 -10) will be analysed using non parametric statistical tests e.g. ANOVA and Mann –Whitney U tests using a PRISM statistical package

The analysis will be carried out by trained post-doctoral senior scientists and [name] at Alcyomics

All data will be coded with regard to the samples from the healthy volunteers.

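### The analysis stated for 6 to 10 donors tests for a group shift and has almost no power for a reaction in a minority of donors; it is not linked to the protocol's donor-level grade II rule

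*Protocol*

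**What the plan says.** **Aim.** The first primary objective (Protocol 2.1) is an assay "that will enable drug sensitivities to be detected at the early stage of drug development".

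**Who reacts.** The Background says that drug hypersensitivity can be linked to a genetic predisposition "occurring in only a minority of the population and therefore can be difficult to predict". It gives no rate.

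**How a reaction is called.** Also in the Background, "a score of a grade II or above is used to predict a positive DHR". The score belongs to one donor, because "the assay is used in an autologous setting, when the different cell types and skin used in the assay are derived from the same donor".

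**How many donors and what analysis.** Section 3.1: "A minimal of 6 volunteers will be tested per compound at various dilutions in order to assess potency and effect of the compound". It continues: "Results from the assays (n=6 -10) will be analysed using non parametric statistical tests", with ANOVA and Mann-Whitney U as examples. Section 3.2 applies the section 3.1 approach to RA Sub-study Group 1 (6 to 10 patients), and section 3.3 runs the surgical samples on the healthy volunteer design.

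The protocol does not say how many of the 6 to 10 donors must reach grade II for a compound to count as positive, or how the grade rule and the group test combine.

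**The concern.** The prediction rule works donor by donor, whereas the tests named in section 3.1 ask whether a whole group has moved. If most donors react, both point the same way. If only some react, which is the pattern the Background warns about, one or two clear reactors among six barely affect a rank or mean comparison.

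The protocol leaves open which result describes the compound when one donor reaches a high grade and the group test is non-significant. For an assay meant to flag sensitivities before human exposure, that is the case that matters most. A result of no reactors needs the same care: six donors may simply contain nobody with the predisposition. Section 5.2 excludes volunteers with evidence of allergy, which may lower the share of reactors among donors further.

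**Working it through.** **Inputs from the protocol.** Minimum 6 donors per compound, analysed as n = 6 to 10 (3.1); positive means grade II or above (Background); autologous assay (Background). No power basis for 6 is given, so there is no planned figure to reproduce.

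**Assumptions, none of them in the protocol.** Two-sided alpha 0.05; a control group of the same size with every control at grade I; reactor shares of 5–20%; for the simulation, a 3 SD shift in reactors and a within-donor correlation of 0 or 0.7.

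**1. Exact test on grade, k of n treated react, 0 of n controls.** If all reactors share one grade and everyone else is at grade I, the exact Mann-Whitney test with ties equals Fisher's exact test.

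| k reacting | n = 6, p | n = 10, p |
|---|---|---|
| 1 | 1.00 | 1.00 |
| 2 | 0.45 | 0.47 |
| 3 | 0.18 | 0.21 |
| 4 | 0.061 | 0.087 |
| 5 | 0.015 | 0.033 |

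At least five donors must react at either size. The chance of five or more reactors is the binomial tail P(X ≥ 5):
- n = 6: 0.01% at a 10% reactor share, 0.2% at 20%.
- n = 10: 0.2% at 10%, 3.3% at 20%.

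**2. Continuous readout, simulated.** Non-reactors are standard normal, reactors are shifted by 3 SD, and an unpaired exact Mann-Whitney test is applied at 10% and 20% reactors.

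| Within-donor correlation | n = 6 | n = 10 |
|---|---|---|
| 0.7 | about 1% and 3% | about 1% and 4% |
| 0 | about 5% and 7% | about 6% and 10% |

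The lower row is close to the false-positive rate of the test, which is about 4% with no reactors and correlation 0. The still lower figures at 0.7 arise partly because an unpaired test ignores the pairing. A stronger reaction does not rescue the test: with a 10 SD shift and correlation 0, power is 4.8% and 7.3% at n = 6, and 5.4% and 10% at n = 10.

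**3. When the same test works.** If every donor shifts by 2 SD, power is 83% at n = 6 and 98% at n = 10.

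**4. What zero reactors shows.** The one-sided 95% upper bound on the reactor share is 1 − 0.05^(1/n).
- 0 of 6: 1 − 0.05^(1/6) = 0.393, or 39%.
- 0 of 10: 1 − 0.05^(1/10) = 0.259, or 26%.

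The chance that six donors include no reactor is (1 − share)^6:
- 5% share: 0.95^6 = 0.74.
- 10% share: 0.90^6 = 0.53.
- 20% share: 0.80^6 = 0.26.

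**The case against.** A reader might infer that a compound with a non-significant group test will be declared free of hypersensitivity risk, or that 0 of 6 will be reported as safe. The protocol says neither. Its only stated prediction rule is the grade, not a p-value, so on its face one grade III donor is a positive prediction whatever the group test shows. That stands, and this point does not allege a wrong decision rule.

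Other parts of the case also stand:
- Section 3.1 ties the donor number to potency across dilutions and also measures lymphocyte proliferation. Location tests are ordinary for such data.
- It is too strong to say that the tests cannot detect a reaction. Step 3 shows good power when most donors respond, and six is a minimum.
- The Background says only that hypersensitivity can be related to a minority predisposition, and it describes non-allergic reactions as the more common and often predictable kind.
- The tests are given as examples, and a separate analysis plan may say more.
- The p-values depend on the method. A tie-corrected normal approximation gives 0.40 for one reactor of six and 0.17 for two, and would call four of six significant (p = 0.025). With six per group and two distinct values the exact test is the appropriate one. One or two reactors are non-significant either way.

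The objection does not remove the mismatch. Section 3.1 is not silent on analysis: it names a family of tests, for all the assay results, and that family is insensitive to the donor-level rule the protocol uses to predict a reaction.

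**Conclusion.** The concern holds as a gap between the donor-level prediction rule and the only stated analysis. Under the assumptions listed, one or two reactors among six give exact p-values of 1.0 and 0.45, at least five reactors are needed at n = 6 or n = 10, and simulated power for 10–20% reactors is about 1–7% at n = 6 and 1–10% at n = 10. The exact values depend on the assumed alpha, control group, shift, reactor share and within-donor correlation, but power stays very low under each of the models tried.

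The bounds of 39% for 0 of 6 and 26% for 0 of 10 require only independent donors, and they refer to people like those enrolled. The documents do not support going further and saying that reactive compounds will be reported as negative. They leave that reading open and give no compound-level rule to prevent it. The change should be made, since it concerns the primary objective and costs little.

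**What to change.** In section 3.1, for the skin-grade endpoint:
- Make the compound-level result the number of distinct donors who are at grade II or above on treated skin with their own untreated control below grade II, over the number of donors tested, with an exact binomial interval. Counting distinct donors matters because each donor supplies several skin pieces, several dilutions are tested, and section 7.6 allows recall.
- Keep location or trend tests for potency across dilutions and for proliferation, and say that they do not decide whether a compound predicts a reaction.
- Report 0 of n with its upper bound (0 of 6: shares above 39% excluded; 0 of 10: above 26%; one-sided 95%), not as a negative prediction.

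Apply the same wording where sections 3.2 (Group 1) and 3.3 rely on section 3.1. The cost is a wording change, with no extra donors, biopsies or blood. The downside is a less favourable claim for compounds with no reactors.
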